15.2 Recording and Reporting AEs, SAEs and SARs

AEs: All AEs that occur from day 1 of laser therapy up to and including the 12 week follow up visit (+/- 1 week) must be recorded on the eCRFs and in the patient medical notes.

The Principal Investigator is responsible for managing AEs at site according to the protocol. Seriousness and relation of the AE to the LLLT treatment should be assessed by the site PI. The Newcastle CTU will maintain a detailed central record of all AEs that occur. There is no requirement to inform sponsor of individual AEs.

SAEs and SARs: All SAEs that occur from day 1 of laser therapy up to and including the 14 month follow up visit (+/- 2 weeks) must be reported to the CI, Newcastle CTU and Sponsor immediately but no later than 24 hours of the site learning of its occurrence. Death should be reported as an SAE if it occurs within this period. If a death occurs after the 14 month visit it does not require reporting as an SAE but must still be recorded in the patient medical notes and eCRFs.

All SARs that occur from day 1 of laser therapy up to and including the end of study, as defined in section 13.10 must also be reported. SARs should be reported using the same process as for SAEs.

The initial SAE report will be made by the site PI completing the agreed SAE form which is sent via SOHO66 (secure fax to email system) to the Senior Trial Manager, Trial Manager, CI and nominated sponsor contact. The initial report can if necessary be made to the Clinical Trials Unit by telephone or e-mail and followed up formally using the SAE form. In the case of incomplete information at the time of initial reporting, or follow up information, a new SAE form must be completed and sent via secure system as soon as possible.

Contact details for reporting SAEs:

Trial Manager, Newcastle Clinical Trials Unit
[name], [contact] [name]

Please send the completed and signed SAE form(s) using the SOHO66 secure network

FAO LITEFORM TRIAL MANAGER to: TBC

All SAEs must be assessed for expectedness using the list of expected adverse events in LiTEFORM Protocol **section 15.2.1** and receive full review by the PI at site and discussed with the CI. It is encouraged that the CI consults with the Chair of the TSC and DMC.

For each SAE the following information will be collected:

• Full details in medical terms and case description

• Event duration (start and end dates, if applicable)

Action taken

Outcome

Seriousness criteria

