15.5 Notification of Deaths

All deaths from day 1 of laser therapy up to and including week 12 follow up will be reported as SAEs irrespective of the cause of death and reported to the sponsor, CTU and CI. All deaths will be reported to the DMC.

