16.1 Statistical Analysis Plan

The primary analysis of the primary outcome is a comparison of the OMWQ-HN score at 6 weeks following start of RT (+/- 2 weeks) in the two randomised arms. Mean baseline and 6-week scores will be presented (with 95% CI) as well as the mean difference from baseline score. Transformation may be appropriate for non-normally distributed data. The null hypothesis to be tested is H0: mean 6-week score in patients randomised to LLLT = mean 6-week score in patients randomised to sham LLLT. Randomisation is stratified by known clinical confounders of cancer treatment: 1. planned treatment (radiotherapy alone or chemo-radiotherapy 2. Unilateral or bilateral radiotherapy fields.

The size and significance of any treatment effect will be estimated in a multivariable linear regression model adjusting treatment by the stratification factor. Secondary analyses of the primary outcome will adjust the size and significance of any treatment effect by other important baseline clinical covariates (importance assessed through univariate modelling) using multivariable regression and ANCOVA. Underlying assumptions of the regression models and non-linear continuous covariates will be investigated, reported and addressed. A two-sided 5% level of significance will be used.

A sensitivity analysis may be carried out on an imputed dataset, based on multiple imputation methods, to deal with missing data and will be described in the Statistical Analysis Plan, which will be

finalised prior to any analysis of unblinded data.

Comparison of secondary outcome measures has not been powered. As such, descriptive statistics such as means (sd, 95% CI), medians (inter-quartile ranges, range) will be presented by randomised treatment arm for continuous secondary outcome measures, specifically scores, feeding tube days, inpatient admission days, water swallow times. ITT proportions (95% CI) will be calculated and presented for categorical measures.

Time to event summary statistics will be estimated using the method of Kaplan and Meier, and 3, 6 and 12-month estimates (with 95% CI) reported. Differences between 'survival' distributions will be estimated using the hazard ratio (95%CI), unadjusted and adjusted by stratification factors.

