1.2.2 Secondary objectives

- Determine the effectiveness of LLLT in preventing severe OM during RT or CRT for HNC as measured by WHO mucositis scores.
- Apply evidence derived from the trial to inform NHS guidance in the use of LLLT for managing OM.
- Investigate the short and long term benefits to patients in terms of dependence on feeding tubes, nutritional status, pain control, admission to hospital, treatment interruptions and swallowing function and quality of life.

- Investigate the long term risks of LLLT (survival, recurrence, disease progression).
- Identify barriers and facilitators to implementing LLLT in routine clinical care through a qualitative process evaluation.

See protocol version 4.0 for further objectives associated with the economic and qualitative sub studies.

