2.4.2 Secondary outcome measures

Note: Data for any 14 month outcomes (marked with asterisk) were only collected for participants who commenced laser therapy prior to 6th July 2018.

WHO Mucositis Oral Toxicity Scale:

The World Health Organisation has developed a grading system for mucositis [2] which measures objective, subjective and functional aspects of OM based on clinical appearance and functional status. The WHO scale is scored on a five point scale, with 0 indicating none, 1 indicating mild, 2 indicating moderate, 3 indicating severe, and 4 indicating life-threatening OM.

The WHO scale was collected by the clinician at baseline, weekly during weeks 1 to 6 of treatment, and at 4 month follow-up.

M.D. Anderson Dysphagia Inventory (MDADI):

The MDADI [3] is patient-reported swallowing outcome measure, specifically designed for the HNC population. The MDADI contains 20 items. Each item on the MDADI follows a five-point response scale ranging from 1 (strongly agree) to 5 (strongly disagree). The MDADI is comprised of four subscales: global (1 item); emotional (6 items); functional (5 items); and physical (8 items). Five scores can be calculated from the MDADI including 2 summary scores (global, total/composite) and 3 subscales (emotional, functional, physical) each calculated as an average with a range of 20 (worst impairment) to 100 (no impairment). The 19-item total (or composite) score will be used to summarize overall impairment on the basis of physical, functional, and emotional domains.

The MDADI was collected at baseline, week 6 of treatment, and at 4 month and 14 month follow-up*.

EORTC-QLQ-C30 (version 3.0) and EORTC-QLQ-H&N35 (version 3.0):

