Modified Intention-to-treat (mITT) analysis set: This population contains all patients randomised into the study (regardless of their adherence with the entry criteria, regardless of subsequent withdrawal from treatment or deviation from the protocol). However, it is a modified ITT analysis set because it will include participants in the treatment group corresponding to the treatment they randomly received (where the randomised (x,y) coordinates for seven participants were used to generate an allocation from the wrong grid).

Statistical analyses will be conducted on complete cases from the mITT analysis set. Participants will be included in analyses if they attended the visit of interest and have evaluable data for the outcome measure of interest. Evaluable data here is non-missing for all outcome measures listed in Section 2.4 except the three questionnaires MDADI, QLQ-C30 and H&N 35, where simple imputation for missing questionnaire items in accordance with the questionnaire’s scoring manual will be used.

Safety population: For the analysis of safety data all randomised patients who received at least one session of laser therapy will be included.

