The number of visits to an oral hygienist over the past seven days will be summarised descriptively as median, interquartile range, and range at each time point for each treatment group. The remaining data will be summarised descriptively as the frequency and percentage at each time point for each of the treatment groups. Data on analgesics will be categorised as no analgesia, simple analgesia (e.g., ibuprofen, paracetamol), opioids (e.g., morphine, oxycodone), and others. Data on mouthwash will be categorised as simple (e.g. FluoriGard, saline, sodium bicarbonate), analgesic (e.g., Difflam), antiseptic (e.g. chlorhexidine), mucosa protecting mouthwash (e.g. Mugard, Gelclair, Caphasol), and others.

Disease outcomes:

Data on disease outcomes collected at 14 months will be summarised descriptively as the frequency and percentage for each of the treatment groups.

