5.5 Missing data

Statistical analyses will be conducted on complete cases from the mITT analysis set. Participants will be included in analyses if they attended the visit of interest and had evaluable data for the outcome measure of interest. Evaluable data here is non-missing for all outcome measures listed in Section 2.4 except the three questionnaires MDADI, QLQ-C30 and H&N 35, where simple imputation for missing questionnaire items in accordance with the questionnaire's scoring manual will be used.

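### Survival remains a long-term risk objective, but the SAP plans no survival analysis, and its one 14-month disease table is, under the general inclusion rule, limited to patients who attended that visit

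*SAP*

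**What the plan says.** SAP 1.2.2 retains the objective "Investigate the long term risks of LLLT (survival, recurrence, disease progression". SAP 2.4.2 describes disease outcomes as a 14-month assessment of recurrence and persistence, without naming death. SAP 5.2 then gives the whole analysis: "Data on disease outcomes collected at 14 months will be summarised descriptively as the frequency and percentage for each of the treatment groups".

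Section 5.2 sets no denominator for this table. The general rule in SAP 3.2 is "Participants will be included in analyses if they attended the visit of interest and have evaluable data for the outcome measure of interest", and SAP 5.5 repeats it: "Statistical analyses will be conducted on complete cases from the mITT analysis set". SAP 2.4.2 adds that 14-month data "were only collected for participants who commenced laser therapy prior to 6th July 2018".

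The supplied protocol (version 2.1) planned more. Section 16 defines survival from randomisation to death from any cause, with survivors censored. It defines time to recurrence from randomisation to clinical recurrence or disease-related death, with other deaths censored. Section 16.1 states: "Time to event summary statistics will be estimated using the method of Kaplan and Meier, and 3, 6 and 12-month estimates (with 95% CI) reported". It also plans hazard ratios with 95% confidence intervals, unadjusted and adjusted for the stratification factors.

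On deaths, Protocol 15.2 sets a serious adverse event period running to the 14-month visit and says "Death should be reported as an SAE if it occurs within this period". Protocol 15.5 says "All deaths from day 1 of laser therapy up to and including week 12 follow up will be reported as SAEs".

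**The concern.** Protocol 8.1 accepts that the laser could worsen tumour behaviour and survival, and undertakes to examine this through recurrence and progression data. This is the trial's main long-term harm question. Under the SAP, survival is an objective without an estimator. Recurrence is compared, if the inclusion rule is followed as written, only among patients alive and present at month 14.

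Conditioning a harm comparison on survival matters when the harm itself can cause death. An arm in which more patients relapse and die early contributes fewer relapses to the attenders' table and can look no worse, or better, than the other arm. Patients who started laser on or after 6 July 2018 add nothing to the table, although SAP 2.6 says all participants were followed to their 4-month visit.

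**Working it through.** **No figure to reproduce.** The plan states no number on this point. The check is a comparison of passages, followed by an illustration with assumed rates.

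**Objective against analysis.**

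| Element | Supplied protocol (v2.1) | SAP |
|---|---|---|
| Survival | Defined with censoring (16); Kaplan-Meier and hazard ratio (16.1) | Objective (1.2.2); no definition or analysis |
| Recurrence | Time to recurrence, defined with censoring (16) | Frequency and percentage at 14 months (5.2) |
| Death at month 14 | Among the data to be recorded (13.6) | Not named under disease outcomes (2.4.2) |
| Deaths in safety reporting | Two periods (15.2, 15.5) | Listing of serious adverse events by arm with onset date (6.2, Table 15); Death rows in adverse event tables, with collection to week 12 (6.1) |

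**Effect of the attendance rule.** Let r be the true proportion with recurrence or death by month 14, and d the proportion dead. Assume that every death follows recurrence or persistence and that every survivor attends. The proportion seen among attenders is (r − d)/(1 − d). The rates below are assumptions.

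| True r, laser v sham | Dead d, laser v sham | Seen, laser | Seen, sham | True difference | Seen difference (points) |
|---|---|---|---|---|---|
| 35% v 25% | 5% v 5% | 0.30/0.95 = 31.6% | 0.20/0.95 = 21.1% | +10 | +10.5 |
| 35% v 25% | 20% v 10% | 0.15/0.80 = 18.8% | 0.15/0.90 = 16.7% | +10 | +2.1 |
| 35% v 25% | 30% v 10% | 0.05/0.70 = 7.1% | 0.15/0.90 = 16.7% | +10 | −9.5 |
| 25% v 25% | 20% v 10% | 0.05/0.80 = 6.3% | 0.15/0.90 = 16.7% | 0 | −10.4 |

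The distortion comes from unequal mortality. With equal 5% mortality it is negligible.

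**What follow-up could support.** The 4-month visit is timed from the end of week 6 of laser therapy (SAP 4.1.2.2). Six weeks is about 1.4 months, so it falls about 5.4 months after laser start. Later starters can therefore contribute to a 3-month survival estimate and be censored afterwards.

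Recurrence is different. Protocol 13.6 lists no recurrence item at month 4, and the schedule in 13.7 marks collection of clinical outcomes during treatment and at month 14 only.

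**Precision of a restored hazard ratio.** With equal allocation, SE(log HR) is about 2/√D for D events, so the 95% interval runs from HR divided by F to HR multiplied by F, where F = exp(1.96 × 2/√D). Power for a true HR of 2 is Φ(ln 2 × √D/2 − 1.96).

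| Assumed events D | F | Power for HR 2 |
|---|---|---|
| 5 | 5.8 | 12% |
| 10 | 3.5 | 19% |
| 20 | 2.4 | 34% |
| 30 | 2.0 | 48% |

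Power of 80% for HR 2 would need 66 events.

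**Table 5 denominator.** SAP Table 5 expresses month-14 follow-up as a percentage of all randomised. Later starters had no month-14 visit to attend, so they would read as losses to follow-up.

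**The case against.** The strongest reply is that the plan does not lose its deaths. Protocol 13.6 lists death among the data recorded at month 14, separately from the visit assessments, so it may be on the form. SAP Table 15 lists serious adverse events by treatment group with onset date, and its severity scale includes death. A reader might infer that deaths vanish from reporting; the documents do not support that. They do leave the deaths without a summary or estimate. The exclusion from the 14-month table is also a consequence of the general rule, since 5.2 is silent. That silence is the defect: nothing in the SAP overrides the rule or adds a category for death.

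A reader might also infer that the SAP departs from its governing protocol. That cannot be shown. The SAP cites protocol version 4.0, which was not available, and that version may have changed the time-to-event plan or the reporting of deaths. What stands is internal to the SAP: it keeps the objective, has no analysis for it and gives no reason.

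It is tempting to ask for time to recurrence in all 87 patients, or for a composite of recurrence or any death. The first assumes recurrence status that the documents do not show was collected for later starters. The second is not the protocol's endpoint, which censors deaths from other causes.

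Finally, secondary outcomes were unpowered, no hypothesis tests on them were planned, and recruitment stopped at 87 of 380. All true, and this limits what any estimate can show. It does not justify a survivor-only comparison.

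**Conclusion.** The concern holds in this form: a retained survival objective has no analysis, and the only disease-outcome table, read with the SAP's own inclusion rule, is conditioned on surviving to and attending month 14. This should be fixed. It does not affect the primary result.

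The size of any distortion is unknown. The documents give no death or recurrence rates and no count of patients who started before 6 July 2018. The illustration ranges from almost no effect to a reversal, depending entirely on assumed mortality by arm. It would be wrong to conclude that the table will mislead in a particular direction. The documents support only that it can, and that the plan has no safeguard against it.

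**What to change.** 1. Add overall survival from randomisation for all 87 patients in the mITT set, with Kaplan-Meier curves by arm and a hazard ratio with 95% confidence interval. Censor at last follow-up and label the result descriptive and imprecise. If protocol version 4.0 removed this analysis, cite the change and its reason, and narrow the objective in SAP 1.2.2 to match.
2. In the 14-month table, take all patients who started laser before 6 July 2018 as denominator. Show death as its own category and include a row for status not known. Use the same denominator for the month-14 row of Table 5.
3. Report time to recurrence under the definition in Protocol 16 only for patients whose recurrence status was recorded. Leave out later starters unless their status was collected.
4. Reconcile Protocol 15.2 and 15.5 on the period for reporting deaths, and state which period sites applied. Item 1 depends on deaths after week 12 having been captured in the same way at every site.

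The cost is SAP wording, one short descriptive analysis and a check that death dates are complete. The downside is a wide interval, about a factor of 3.5 either way with an assumed 10 events, which must not be read as evidence of safety.

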5.3 Planned subgroup analyses

In order to inform future studies the OMWQ-HN score at week 6 will be summarised descriptively within each stratification subgroup:

1. planned treatment (radiotherapy alone or chemo-radiotherapy)
2. unilateral or bilateral radiotherapy fields.

5.4 Additional / Exploratory Analyses

Intraoral photographs

WHO Mucositis Oral Toxicity Scale assessments based on photographs taken at the 4 month visit will be summarised descriptively as the frequency and percentage for two collapsed categories 0-I (none to mild) and II-IV (moderate to life-threatening) based on the reasoning that it would not be possible to discriminate between the grades further from a photograph [agreed at the TMG on 24.10.19]. The two WHO assessments (based on looking in the participant's mouth and based on the assessment of the photographs) will be cross-tabulated.

5.5 Missing data

Statistical analyses will be conducted on complete cases from the mITT analysis set. Participants will be included in analyses if they attended the visit of interest and had evaluable data for the outcome measure of interest. Evaluable data here is non-missing for all outcome measures listed in Section 2.4 except the three questionnaires MDADI, QLQ-C30 and H&N 35, where simple imputation for missing questionnaire items in accordance with the questionnaire's scoring manual will be used.

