16.4 Sample Size Calculations

A total of 380 patients will be recruited from ten head and neck cancer treatment centres across England and Wales. A minimum of 100 patients will be recruited during the pilot phase of the trial with the remaining patients being recruited within the main trial phase.

The primary outcome measure is OMWQ-HN score at 6 weeks following start of irradiation. According to Epstein 2007, a group difference of 4 points would reflect a meaningful treatment effect. Epstein also reported variability in the QMWQ-HN as a standard deviation of 10.7. As a definitive trial, LITEFORM is powered with small and acceptable errors of 5% α and 10% β . With these parameters, a total of 152 patients with primary outcome data are required in each treatment group to be able to detect this size of clinically relevant difference with 90% power. The trial team estimate there will be patient drop out, hence the sample size is inflated to 190 patients recruited in each trial arm assuming a maximum of 20% drop-out or missing data. This sample size was calculated using the *power two means* option in Stata (version 13.1) and validated using Julious 2009. The underlying assumptions of the sample size will be monitored by the external Data Monitoring Committee.

17. Qualitative Sub-Study

The qualitative process evaluation will will employ a combination of qualitative research techniques, including formal (audio-recorded) face-to-face and telephone interviews, non-participating observation of launch meetings, site initiation visits and training sessions, and audio-recorded recruitment/consent discussions. Non-participant observation involves the production of contemporaneous field notes from which analytic themes will be identified. Interviews and recruitment/consent discussions will be audio-recorded with the respondent's consent, transcribed and edited to ensure anonymity of respondent. The anonymisedranscripts will be then subjected to formal analysis. Because of the large number of interviews, field-notes, and recordings of discussions

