5. ANALYSIS METHODS

5.1 Primary outcome

Definition of the primary outcome:

The primary outcome is the OMWQ-HN score at week 6 following start of LLLT treatment.

Primary outcome measure

The primary outcome measure is the OMWQ-HN score. The OMWQ-HN was collected at baseline, weekly during weeks 1 to 6 of treatment, and at 4 month follow-up.

[figure not shown]
Responses to the OMWQ-HN will be summed to give a total overall score between 0 and 54 (a higher score indicating poorer wellbeing and oral function). The total score will not be computed for participants who had missing data on ≥ 1 item, with the exception of participants who scored '0' (=no soreness) on question 1 (who would not then proceed to the remaining questions and would be given a total score of 0).

Example Table 8: Completeness of primary outcome data by visit and treatment group

	Laser			Sham			Total					
	n	Fully missing	Partial missing	Complete	n	Fully missing	Partial missing	Complete	n	Fully missing	Partial missing	Complete
Baseline												
Week 1												
Week 2												
Week 3												
Week 4												
Week 5												
Week 6												
4 month												

The OMWQ-HN will be explored graphically using individual participant plots over time and at 6 weeks using histograms or dotplots and/or boxplots by treatment group. The OMWQ-HN will be summarised numerically as mean, standard deviation, median, interquartile range, and range at each time point for each of the treatment groups.

Example Figure 4: Individual participant plots of OMWQ-HN by visit [baseline to week 6]

Example Table 9: Summary statistics for OMWQ-HN over time

Laser								
	Baseline (n =)	Week 1 (n =)	Week 2 (n =)	Week 3 (n =)	Week 4 (n =)	Week 5 (n =)	Week 6 (n =)	4 Month (n =)
Min								
Median (IQR)								
Mean (SD)								
Max								
Sham								
	Baseline (n =)	Week 1 (n =)	Week 2 (n =)	Week 3 (n =)	Week 4 (n =)	Week 5 (n =)	Week 6 (n =)	4 Month (n =)
Min								
Median (IQR)								
Mean (SD)								
Max								
Higher scores on the OMWQ-HN indicate poorer wellbeing and oral function.								

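### The week-6 OMWQ-HN difference rests on complete cases alone: the SAP puts the week 1-5 scores to no inferential use and plans no missing-data sensitivity analysis

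*SAP*

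**What the plan says.** SAP 3.2 and 5.5 set one rule for all outcomes: "Statistical analyses will be conducted on complete cases from the mITT analysis set". A participant enters an analysis if the visit was attended and the outcome is evaluable. For the primary score, SAP 5.1 adds: "The total score will not be computed for participants who had missing data on ≥ 1 item". The exception is a zero on question 1, which gives a total of 0. Simple item imputation is allowed for the MDADI, QLQ-C30 and H&N35, but not for the OMWQ-HN.

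The primary analysis (SAP 5.1.1) is the unadjusted difference in week-6 means with a 95% confidence interval. The secondary analysis (SAP 5.1.2) is ANCOVA on baseline, for those with both baseline and week-6 scores. SAP 5.1 also records: "The OMWQ-HN was collected at baseline, weekly during weeks 1 to 6 of treatment, and at 4 month follow-up". The week 1-5 scores appear only in individual plots and summary statistics.

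The protocol had already put the primary analysis on a complete-case basis (section 16). It allowed for more if missing data made it necessary: "A sensitivity analysis may be carried out on an imputed dataset, based on multiple imputation methods, to deal with missing data" (16.1), with the description left to the SAP. Section 16.1 also mentions possible exploratory hierarchical modelling of repeated measures. The SAP contains neither.

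**The concern.** A participant who misses week 6, or leaves one item blank, drops out of both estimates even if several earlier weekly scores are on file. Those scores carry information about the missing value.

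Loss related to severity is plausible on the protocol's own account. Section 7 says that patients may be too unwell to attend (C)RT sessions, and section 13.8 lists symptomatic deterioration among the reasons for discontinuation. The design allowed for up to 20% loss, and the pilot criterion in section 10 accepted 80% completion at week 6.

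With 87 participants, the estimate and its interval are the trial's main product. As the SAP stands, nothing shows a reader how far they depend on who supplied a week-6 score.

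**Working it through.** **1. The plan's own figure.** Inputs from Protocol 16.1 and 16.4: "A two-sided 5% level of significance will be used"; "detect this size of clinically relevant difference with 90% power"; "a group difference of 4 points would reflect a meaningful treatment effect"; variability given "as a standard deviation of 10.7".

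- Normal approximation: n per arm = 2 × (1.960 + 1.282)² × 10.7² / 4² ≈ 150.4, so 151.
- Noncentral t: power is 0.8994 at 151 and 0.9012 at 152, so 152 per arm, as stated.
- Inflation: 152 / 0.80 = 190 per arm, as stated.

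**2. Precision at the achieved size.** SAP 2.6 gives 87 randomised, or 43.5 per arm on average. Let m be the share missing week 6 and ρ the correlation of the weekly history with week 6. Neither is in the documents; m = 10-30% and ρ = 0.5-0.8 are assumed, with missingness at random.

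- Complete case: Var = 2 × SD² / [n(1 − m)]
- Using the history: Var = (2 × SD² / n) × [1 + (m / (1 − m)) × (1 − ρ²)]

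Here 2 × 10.7² / 43.5 = 5.264. At m = 0.20, complete case gives √(5.264 / 0.80) = 2.57. With ρ = 0.7, the history gives √(5.264 × [1 + 0.25 × 0.51]) = 2.44.

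| Missing | SE, complete case | SE with history, ρ = 0.5 / 0.7 / 0.8 | Reduction |
|---|---|---|---|
| 10% | 2.42 | 2.39 / 2.36 / 2.34 | 1-3% |
| 20% | 2.57 | 2.50 / 2.44 / 2.40 | 2.5-7% |
| 30% | 2.74 | 2.64 / 2.53 / 2.47 | 4-10% |

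At 20% missing, the 95% half-width falls from 5.1 to 5.0-4.8, and power for 4 points rises from about 34% to 36-39%. With nothing missing, the half-width would still be 4.6 and power about 41%.

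**3. Bias in the difference (sham minus laser).** This comes from large-sample simulation with SD 10.7 and logistic missingness. The odds of missing week 6 are multiplied by 2 to 3 per SD of severity. The week 5-6 correlation is 0.7 unless stated. All of these except the SD are assumptions.

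| Scenario | Bias, missingness on week 5 | Bias, missingness on week 6 |
|---|---|---|
| Common mechanism, no true effect | 0 | 0 |
| 20% lost in each arm, same severity slope | 0 | 0 |
| Common mechanism, true effect 4, about 20% lost overall | −0.15 to −0.30 | −0.28 to −0.50 |
| 30% lost in sham, 10% in laser | −0.9 to −1.3 | −1.3 to −1.9 |

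For the third row with missingness on week 5, varying the correlation over 0.6-0.8 gives estimates of 3.6 to 3.85, a bias of about 0.15 to 0.4. If severity predicts loss more steeply in sham than in laser, the estimate falls to 2.2-3.1 against a true 4, a bias of 0.9 to 1.8. Reaching about 2.2 took odds of roughly 3 to 5 per SD in sham and no severity link in laser.

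**4. What the weekly scores recover.** Predicting the missing week-6 score from week 5 within arm removes the bias when missingness depends on week 5. When it depends on the unseen week-6 score, only about 45% is removed. For example, with a true effect of 4 and 30% versus 10% lost, the bias goes from −1.33 to −0.72.

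**The case against.** Complete case is the protocol's own basis for the primary analysis, and the imputed analysis was optional and conditional. A reader might infer that the SAP removed a committed analysis. The documents do not support that: an option was not taken up, and no reason is given. The SAP also cites protocol version 4.0 while the protocol supplied is version 2.1, so a later change cannot be excluded.

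A reader might also infer that the estimate must be biased once sicker patients miss week 6, or that complete case is valid only if missingness is unrelated to earlier scores. For the between-arm difference neither follows. Such loss shifts both arm means and largely cancels unless the arms differ in loss, in its link to severity, or in outcome. Losses of a quarter to nearly a half of a 4-point effect need the loss, or its slope on severity, to differ clearly between arms. The documents give no reason to expect that in a blinded, sham-controlled trial.

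The plan also has real protections:

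- a completion window of one week before to two weeks after for the week-6 questionnaire (Protocol 13.6);
- follow-up after withdrawal from treatment (13.8);
- data collection from inpatients (14.1);
- the ANCOVA, which covers missingness that depends on baseline score;
- a completeness table by visit and arm (SAP Table 8).

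All of this stands, and it limits the size of the point. It does not fill the gap: no planned analysis uses the post-baseline history or tests the missingness assumption.

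**Conclusion.** The point holds as an omitted sensitivity analysis and a modest inefficiency. At an assumed 20% missing, the complete-case rule gives up 2.5-7% in standard error; at 10%, the lower end of the dropout range expected in Protocol 13.8, it gives up 1-3%. The trial's imprecision comes mainly from recruiting 87 instead of 380.

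The bias is conditional, as the table above shows. Under one common mechanism linked to week 5 and a true effect of 4, it is small beside a standard error near 2.5. It reaches 1-2 points only with a clear difference between arms, and it would then work against laser even if there were no true effect. The actual week-6 missingness, its pattern, and the share of non-completers with recent scores are not in the documents, so every figure here except the reproduced sample size rests on assumed inputs.

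**What to change.** Keep the planned complete-case difference and add to the SAP:

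1. A prespecified repeated-measures model of OMWQ-HN at weeks 1-6, with arm by week, baseline by week and the two stratification factors, reporting the week-6 contrast. Specify an unstructured covariance, a named simpler structure if it fails to converge, and a small-sample degrees-of-freedom correction. Multiple imputation by arm from baseline and weeks 1-5 would be an acceptable alternative. Do not simply enter the week-5 score as a covariate: treatment may already have affected it, and adjusting for it would remove part of the effect.
2. A delta-adjusted sensitivity analysis, because item 1 only partly corrects for missingness that depends on the unseen week-6 score.
3. A table of week-6 missingness by arm and last observed score.

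The cost is SAP wording and a little more analysis in software already in use, with no new data. Item 1 relies on data being missing at random given the weekly history, an assumption to be stated with the result.
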